## **5.6.2 Pembrolizumab Administration**

Pembrolizumab will be administered by intravenous infusion in accordance with KEYTRUDA® Prescribing Information (Package Insert and institutional practice either as 200 mg on Day 1 of every cycle or 400 mg on Day 1 of every other cycle (Cycle 1, 3, 5, etc.). If administration of HBI-8000 is delayed or interrupted due to an AE not attributed to pembrolizumab, administration of pembrolizumab will not be affected.

To manage infusion reactions, pembrolizumab will be administered only at sites that are fully equipped to handle infusion reactions, and with study personnel that are properly trained.

### **5.6.2.1.1 Pembrolizumab Dose Modifications**

Dose modifications for pembrolizumab should be followed according to the most recent approved label for KEYTRUDA®, therefore, withhold or permanently discontinue pembrolizumab for adverse events as outlined in the KEYTRUDA US package insert (USPI) as per its use in non-small cell lung cancer.

In the event that pembrolizumab is discontinued (for reasons other than immune-mediated reactions), HBI-8000 may be continued until one of the conditions for HBI-8000 discontinuation is met at the Investigator's discretion in consultation with Sponsor Medical Monitor.

### **5.6.2.1.2 Pembrolizumab Dose Delay Independent of HBI-8000 Administration**

Investigators should withhold a dose as described in the KEYTRUDA USPI (Recommended treatment modifications) until it is reduced to a Grade 1 or resolved. Once resolved, the dose may be reinstated. For subjects who were treated with steroids for irAE, steroids need to be tapered to

a dose 10 mg or less of prednisone or equivalent over at least 1 month before resuming pembrolizumab. The administration of HBI-8000 may continue as scheduled during pembrolizumab dosing interruption.

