## STUDY SYNOPSIS

Name of Sponsor/ Company:	HUYABIO International, LLC
Name of Finished Product:	HBI-8000 (tucidinostat)
Name of Active Ingredient:	N -(2-amino-4-fluorophenyl)-4-{{(2E)-3-(pyridin-3-yl)prop-2-enamido]methyl}benzamide
Title of Study:	A Phase 2 Study to Assess the Safety and Efficacy of HBI-8000 in Combination with Pembrolizumab for Advanced or Metastatic Non-Small Cell Lung Cancer (NSCLC)
Protocol No:	HBI-8000-305
Lead Investigator:	[name]
Indication	Advanced or Metastatic NSCLC
Study Population	Subjects $\geq 18$ years of age with advanced or metastatic NSCLC who have not received immune checkpoint inhibitor for their disease but have programmed death ligand 1 (PD-L1) expression Tumor Proportion Score (TPS): $\geq 1\%$ .
Study center(s):	Multicenter study (US): 6-10
Study duration:	Approximately 38 months (including follow-up)  The study will include a screening period (up to 28 days), up to 24 months of treatment of HBI-8000 with pembrolizumab, up to 1 month post-treatment follow-up for safety, and up to 12 months after the last dose of HBI-8000 for survival follow-up by telephone calls/e-mails.
Phase	2
Study Treatment	HBI-8000 tablets 30 mg/dose, orally twice a week  An HBI-8000 treatment cycle consists of twice a week dosing over 21 consecutive days. Pembrolizumab will be administered at 400 mg every 6 weeks or 200 mg every 3 weeks according to Prescribing Information and institutional practice.  Treatment will continue until disease progression or unacceptable toxicity occurs. Should toxicity be deemed not related to pembrolizumab but HBI-8000, subject may continue to receive pembrolizumab under standard of care. Should toxicities be deemed related to pembrolizumab, the subject may continue receiving HBI-8000 at the discretion of Investigator.

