Pembrolizumab is a humanized IgG4 anti-PD-1. Various dosing regimens of pembrolizumab were evaluated in the Phase 1b study KEYNOTE 001 in 101 patients with treatment-naïve NSCLC. The most common treatment related AEs were fatigue (27.7%), followed by pruritus (14.9%), hypothyroidism (13.9%), rash (13.9%), arthralgia (11.9%), and nausea (11.9%). However, Grade 3/4 treatment-related AEs occurred in 12% subjects [Hui 2017]. The immune-mediated AEs, regardless of attribution to treatment as reported by investigators, were observed in 22% of patients, with hypothyroidism being most common in 15% of patients. All were of grade 1 or 2 severity, except for 1 case each of grade 3 pneumonitis, hypophysitis, colitis, and dermatitis, manageable with steroids and supportive care. There were no treatment-related deaths. Efficacy was apparent in all treatment regiments and was more prominent in tumors with higher PD-L1 expression.

KEYNOTE 010, a phase 2/3 study, further evaluated the efficacy and safety of pembrolizumab at 2 and 10 mg/kg given every 3 weeks (Q3W) in previously treated NSCLC. This study demonstrated superior overall survival (OS) over standard-of-care docetaxel treatment in patients with previously treated, PD-L1-positive NSCLC [Herbst 2016]. Improvement of PFS and ORR over docetaxel were also evident in all patients with positive PD-L1 expression status assessed by an immunohistochemical assay reported as tumor proportion score (TPS)  $\geq 1\%$  of either

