### 1.1.3.3 HBI-8000 Safety Profile

As a monotherapy, the main safety findings for HBI-8000 are myelosuppression (thrombocytopenia, neutropenia, leukopenia, and anemia) observed in heavily pre-treated relapsed and refractory T-cell lymphoma patients. Additional toxicities included gastrointestinal symptoms, fatigue and asymptomatic laboratory abnormalities. Toxicities were generally mild and manageable with supportive care, dose reductions, interruption, or delays.

In clinical studies, treatment with HBI-8000 has been associated with exposure-related myelosuppression, categorized as important identified risk and includes thrombocytopenia, anemia, and neutropenia or lymphopenia. These myelosuppression related toxicities were more severe in patients with relapsed and refractory hematological malignancies than in patients with solid tumors. In general, the hematologic AEs are manageable with supportive care such as hematological growth factor administration, dosing interruption and dose reduction. Other important identified risks are pneumonitis, interstitial lung disease, and interstitial pneumonia.

In the HBI-8000-302 study, the safety of HBI-8000 administered in combination with standard dose immune checkpoint inhibitor (CPI), nivolumab, has been evaluated in 89 patients total including 49 with melanoma, 29 with NSCLC and 11 with renal cell carcinoma. The most common AEs of all grades associated with HBI-8000 were fatigue (59.6%), thrombocytopenia (49.4%), nausea (48.3%), diarrhea (47.2%), anemia (42.7%), dyspnea (37.1%), peripheral edema (33.7%), anorexia (32.6%), neutropenia (31.5%) and leukopenia (31.6%). The most reported Grade 3 or higher adverse events were lymphopenia, neutropenia, hypophosphatemia, fatigue, anemia and diarrhea. Only 3 subjects had transaminase elevation were reported as Grade 3. The safety profiles so far have been consistent with those observed in HBI-8000 monotherapy, although the hematological toxicities were less severe and less frequent, as expected with solid tumor patient population. There has been no evidence of increased risk for immune-related toxicity over those expected with nivolumab treatment alone.

Arrhythmia including QTc prolongation may occur and are categorized as important potential risk. However, recently, a QT interval corrected by heart rate (QTc) **HBI-8000-302**

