### **4.5 Discontinuation of Investigational Product and Participant Withdrawal**

Subjects discontinued from HBI-8000 for toxicity in the absence of disease progression may continue to receive pembrolizumab under standard of care and be followed for disease response as long as consent to study participation remains effective. Similarly, if pembrolizumab administration is discontinued due to unacceptable toxicities (other than immune-mediated reactions) associated with pembrolizumab, the subject may continue to receive HBI-8000, at the Investigator's discretion in consultation with Sponsor Medical Monitor and be followed for disease response as long as consent to study participation remains effective. When both HBI-8000 and pembrolizumab have been discontinued and disease has not progressed, the subject will continue to be followed for disease status in the Follow-up Phase until evidence of progression.

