**C. Immune-related AEs (irAE)**

- Any Grade 2 or greater eye pain or reduction in visual acuity that does not respond to topical therapy and does not improve to Grade 1 severity within 2 weeks of the initiation of topical therapy or any Grade 2 or greater eye pain or reduction in visual acuity that requires systemic treatment.
- Any other Grade 3 or greater irAE

If pembrolizumab is withheld or permanently discontinued due to an immune-mediated reaction, HBI-8000 should be withheld or permanently discontinued, respectively.

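### Section 5.6.2.1.2 lets HBI-8000 continue during any pembrolizumab interruption, which conflicts with the rule in 5.6.1.1 C to withhold it when the interruption is for an immune-mediated reaction

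*Combined protocol and SAP*

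**What the plan says.** Section 5.6.2.1.2 deals with withholding pembrolizumab under its US label. For subjects given steroids for an immune-related event, it requires a taper to "a dose 10 mg or less of prednisone or equivalent over at least 1 month before resuming pembrolizumab". The next and last sentence reads "The administration of HBI-8000 may continue as scheduled during pembrolizumab dosing interruption". It states no exception by cause and does not refer to 5.6.1.1.

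Section 5.6.1.1 C, under HBI-8000 dose reduction, closes with the opposite instruction: "If pembrolizumab is withheld or permanently discontinued due to an immune-mediated reaction, HBI-8000 should be withheld or permanently discontinued, respectively".

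Two other sections let HBI-8000 go on after pembrolizumab is stopped, and both carve out immune-mediated reactions. Section 4.5 says "if pembrolizumab administration is discontinued due to unacceptable toxicities (other than immune-mediated reactions) associated with pembrolizumab, the subject may continue to receive HBI-8000", in consultation with the Sponsor Medical Monitor. Section 5.6.2.1.1 has the same exception and the same consultation. Both speak of discontinuation, not of a temporary hold.

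The synopsis (Study Treatment) has neither the exception nor the consultation: "Should toxicities be deemed related to pembrolizumab, the subject may continue receiving HBI-8000 at the discretion of Investigator".

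**The concern.** An investigator who holds pembrolizumab for an immune-mediated reaction would naturally turn to the section on pembrolizumab delays. That section allows HBI-8000 on schedule. The instruction to withhold it sits in a different section, on HBI-8000 dose reduction. Two sites treating the same event could therefore dose differently, and each could point to protocol text in support.

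What is at stake is exposure to HBI-8000 during an immune-mediated reaction, when another safety rule says it should not be given. Lung toxicity is where the two drugs' risks plausibly overlap. For HBI-8000, Section 1.1.3.3 says "Other important identified risks are pneumonitis, interstitial lung disease, and interstitial pneumonia", and the population has lung cancer.

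**Working it through.** The plan gives no figure to reproduce here. The check compares the rules for one case, pembrolizumab temporarily withheld for an immune-mediated reaction, and then makes one dose count.

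**Step 1: what each section tells the site to do with HBI-8000**

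| Section | Event covered | Instruction for HBI-8000 | Immune-mediated exception |
|---|---|---|---|
| 5.6.1.1 C, last sentence | Pembrolizumab withheld or stopped for an immune-mediated reaction | Withhold or stop, to match | This is the rule itself |
| 5.6.2.1.2, last sentence | Pembrolizumab interruption | May continue on schedule | None |
| 4.5 | Pembrolizumab discontinued for toxicity | May continue, with Medical Monitor consultation | Yes |
| 5.6.2.1.1 | Pembrolizumab discontinued | May continue, with Medical Monitor consultation | Yes |
| Synopsis | Toxicity related to pembrolizumab | May continue at Investigator discretion | None |

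Only the first two rows speak directly to a temporary hold, and they disagree. Section 5.6.2.1.2 cannot be read as confined to non-immune causes: immune-related events are the only type of toxicity it names, and it names them in the sentence just before the permission.

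**Step 2: where 5.6.1.1 C is the only safeguard**

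- *Grade 3 or higher immune-related events, and the listed eye events.* These are dose-reduction triggers in 5.6.1.1 C. Under 5.6.1.1, HBI-8000 resumes only at a reduced dose and only after return to Grade 1 or less within 14 days. For non-hematological toxicity a single reduction is allowed, from 30 mg to 20 mg. Section 5.6.2.1.2 could then add only reduced-dose HBI-8000 during the rest of the pembrolizumab hold.
- *Other immune-mediated reactions below Grade 3 that lead to a pembrolizumab hold.* They meet none of those triggers. The last sentence of 5.6.1.1 C is the only rule in 5.6.1.1 that withholds HBI-8000, and it is the rule that 5.6.2.1.2 contradicts. Full-dose HBI-8000 is the exposure in question.

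**Step 3: doses per affected subject treated with steroids**

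Inputs: twice-weekly dosing (5.6.1); a taper of at least one month before pembrolizumab resumes (5.6.2.1.2), taken as 30 days.

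Doses = 30 × 2/7 = 8.6, so 8 or 9. A longer taper gives more.

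**Step 4: number of subjects**

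This needs the rate of pembrolizumab holds for immune-mediated reactions, which the documents do not give. Section 5.6.2.1.1 leaves that decision to the US label. The nearest figure is for pembrolizumab alone in 101 patients (Section 1.1.1), where immune-mediated events "were observed in 22% of patients, with hypothyroidism being most common in 15% of patients". That is an incidence of events, not of holds. If none led to a hold, the expected number affected is 0. If all did, it is 20 × 0.22 = 4.4 to 24 × 0.22 = 5.3 subjects. Both ends are assumptions, and a range this wide amounts to not knowing.

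**The case against.** The best defence is that the specific rule governs the general one. Section 5.6.1.1 C is tied to a cause and says should; 5.6.2.1.2 is general and says may. A careful investigator who reads both would withhold. That is reasonable, but it relies on the reader finding both sections. There is no cross-reference and no statement of which prevails.

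Some text also tempers the harm. Section 5.6.1.2 lets the Investigator delay HBI-8000 for up to 14 days for toxicity possibly or probably related to it. Section 1.1.3.3 reports no evidence that immune-related toxicity with nivolumab exceeded that expected from nivolumab alone. Neither removes the conflict. The delay is optional, depends on attribution to HBI-8000, and covers 14 × 2/7 = 4 doses, against 8 to 9 in the taper. The nivolumab experience does not say which instruction to follow.

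A reader might go further than the documents allow in several ways:

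- *That 5.6.2.1.2 and the synopsis override 5.6.1.1 C.* Nothing gives them precedence; they conflict with it.
- *That 4.5 and 5.6.2.1.1 settle the intent.* They cover discontinuation only, so they support 5.6.1.1 C by analogy.
- *That the Grade 3 pneumonitis case in Section 1.1.1 shows the gap.* A Grade 3 event is already caught by the other rules in 5.6.1.1, and no count of lower-grade pneumonitis is given. A rate built from the four Grade 3 cases reported there would count the wrong subjects for the same reason.
- *That the synopsis makes the same error.* It addresses toxicity attribution and does not mention dose interruption. It omits an exception, which is secondary.

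**Conclusion.** The conflict is real and should be corrected. For a temporary pembrolizumab hold due to an immune-mediated reaction, 5.6.2.1.2 permits what 5.6.1.1 C says should not be done, and no other section reconciles them. The main exposure is in reactions below Grade 3, other than the listed eye events. For Grade 3 and above, the remaining conflict is limited to reduced-dose HBI-8000 after recovery.

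Per affected subject given steroids, about 8 to 9 scheduled doses are in dispute, assuming a 30-day taper and no other reason to hold HBI-8000. How many subjects that would be cannot be estimated from the documents, and the conclusion does not depend on it. Nor do the documents show that continuing HBI-8000 worsens an immune-mediated reaction; the point is that the protocol says both to withhold it and that it may continue.

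There is no consequence for the definition or analysis of ORR, DCR, DoR or PFS.

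**What to change.** 1. In 5.6.2.1.2, limit the last sentence to a pembrolizumab interruption *that is not due to an immune-mediated reaction (see 5.6.1.1 C)*.

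2. Secondary: in the synopsis (Study Treatment), extend the sentence on pembrolizumab-related toxicity so that Investigator discretion is exercised *in consultation with the Sponsor Medical Monitor, except when pembrolizumab is withheld or permanently discontinued due to an immune-mediated reaction (see 5.6.1.1 C)*. This brings it into line with 4.5 and 5.6.2.1.1 on both counts.

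The cost is two sentences in a protocol amendment. Neither change creates a new stopping rule, and procedures, visits, sample size and analysis stay as they are.

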## **3 STUDY DESIGN**

### **3.1 Overall Design**

This is a multicenter, open label, non-randomized, Phase 2 study of HBI-8000 in combination with a Food and Drug Administration (FDA) approved dose of pembrolizumab as the first checkpoint inhibitor therapy for advanced or metastatic NSCLC where subjects have programmed death ligand 1 (PD-L1) expression Tumor Proportion Score (TPS)  $\geq 1\%$ . Prior to enrollment, the PD-L1 expression status must be available. Historical data may be used to assess for eligibility. If historical data is not available, tumor tissue will be analyzed locally by an FDA-approved test to yield PD-L1 status prior to enrollment.

The dose of HBI-8000 is 30 mg twice weekly. Pembrolizumab is administered according to prescribing information.

The study will include a screening period of up to 28 days before the first dose of HBI-8000. Study Treatment may be with or without pembrolizumab. HBI-8000 and pembrolizumab will continue up to 24 months. HBI-8000 will continue until disease progression, unacceptable toxicity related to HBI-8000 ensues or withdrawal of informed consent to receive HBI-8000.

The Treatment Phase allows for up to 24 months of treatment (cycles are 21 days), providing the subject does not experience disease progression or unacceptable toxicity. An End of Treatment safety visit will be performed 30 ( $\pm 3$ ) days after last dosing of HBI-8000. If HBI-8000 is discontinued due to unacceptable toxicities related to HBI-8000, pembrolizumab may continue as single agent under standard of care. Subjects will be followed for up to 12 months after the last dose of HBI-8000 for disease status, including initiating a new cancer treatment and experiencing disease progression, death, or becoming lost to follow-up or consent withdrawal.

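### Section 5.6.2.1.2 permits scheduled HBI-8000 during any pembrolizumab interruption, against the hold that Section 5.6.1.1 C sets for immune-mediated reactions, and the Synopsis also lacks that exception

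*Combined protocol and SAP*

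**What the plan says.** **Pembrolizumab holds.** Section 5.6.1.1 C, within the HBI-8000 dose-reduction rules, states: "If pembrolizumab is withheld or permanently discontinued due to an immune-mediated reaction, HBI-8000 should be withheld or permanently discontinued, respectively". Section 5.6.2.1.2 tells investigators to withhold pembrolizumab as its US label describes. For subjects given steroids for an irAE, it requires a taper to "a dose 10 mg or less of prednisone or equivalent over at least 1 month before resuming pembrolizumab". Its next and last sentence is: "The administration of HBI-8000 may continue as scheduled during pembrolizumab dosing interruption". That sentence has no exception and no cross-reference.

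**Pembrolizumab discontinuation.** Section 4.5 lets HBI-8000 go on when pembrolizumab is "discontinued due to unacceptable toxicities (other than immune-mediated reactions) associated with pembrolizumab". Section 5.6.2.1.1 says the same: "In the event that pembrolizumab is discontinued (for reasons other than immune-mediated reactions), HBI-8000 may be continued". Both require consultation with the Sponsor Medical Monitor. The Synopsis, under Study Treatment, has neither condition: "Should toxicities be deemed related to pembrolizumab, the subject may continue receiving HBI-8000 at the discretion of Investigator".

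**Related rules.** The Section 5.6.1.1 C list of events that lead to HBI-8000 dose reduction names certain Grade 2 or greater eye events and "Any other Grade 3 or greater irAE". The paragraph that closes Section 5.6.1.1 is printed under item D but worded generally. It allows HBI-8000 to resume only at a reduced dose, after recovery to Grade 1 or less within 14 days of the toxicity.

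**The concern.** An investigator managing a pembrolizumab hold would naturally open Section 5.6.2, the pembrolizumab section. There, straight after the steroid-taper rule for irAEs, the protocol gives written permission to keep dosing HBI-8000. The instruction to hold it sits in a different section, as the closing sentence of a sub-item on HBI-8000 dose reduction. Two sites with the same event could treat it differently, each with protocol text in support.

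Section 1.1.3.3 lists pneumonitis and interstitial lung disease among the important identified risks of HBI-8000 itself. Whether HBI-8000 is given while pembrolizumab is off for such a reaction is therefore a safety instruction. Section 7.4.2 plans summaries of HBI-8000 compliance and relative dose intensity, so sites applying different rules would also record different exposure for similar events.

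**Working it through.** No figure in the plan depends on this point, so there is none to reproduce. The first check sets the sections side by side; the second counts what the difference could amount to for one subject.

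**Side by side: what happens to HBI-8000**

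| Situation | Section 5.6.1.1 C | Other body sections | Synopsis |
|---|---|---|---|
| Pembrolizumab held, immune-mediated reaction | Withhold | 5.6.2.1.2: may continue | May continue |
| Pembrolizumab held, other toxicity | Linked hold does not apply | 5.6.2.1.2: may continue | May continue |
| Pembrolizumab stopped, immune-mediated reaction | Stop | 4.5 and 5.6.2.1.1: permission excludes this case | May continue |
| Pembrolizumab stopped, other toxicity | Linked stop does not apply | 4.5 and 5.6.2.1.1: may continue, Medical Monitor consulted | May continue, no consultation |

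The Synopsis column assumes toxicity attributed to pembrolizumab. Its sentence speaks of such toxicity in general and does not mention discontinuation, so it covers all four rows. Rows 1 and 3 are the conflicts. Row 4 is an omission. Row 2 is consistent.

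**Which subjects the row 1 conflict reaches**

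1. For Grade 3 or greater irAEs, and the listed eye events, Section 5.6.1.1 already requires a dose reduction. If its closing paragraph applies to irAEs, as its general wording suggests, dosing resumes only after recovery to Grade 1 or less within 14 days. A subject who has not recovered in that time does not meet the resumption condition, whatever Section 5.6.2.1.2 says.
2. For other irAEs below Grade 3 that lead to a pembrolizumab hold, the linked-hold sentence in Section 5.6.1.1 C is the only irAE-specific hold rule for HBI-8000. This is the group for which Section 5.6.2.1.2 makes most difference. Which irAEs these are is set by the US label, which is not reproduced in the protocol.

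**Doses per subject in that second group**

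Inputs: twice-weekly dosing at 30 mg (Section 5.6.1) and a taper of at least 1 month (Section 5.6.2.1.2). Assumptions: a month is 28 to 31 days, and under Section 5.6.1.1 C HBI-8000 stays off for as long as pembrolizumab does.

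- Doses = days / 7 × 2. For 28 days: 28 / 7 × 2 = 8.0. For 31 days: 31 / 7 × 2 = 8.9.
- In whole doses on a Monday/Thursday or Monday/Friday schedule: 8 in 28 days, and 8 or 9 in 30 or 31 days depending on the start day.
- Amount: 8 × 30 = 240 mg; 9 × 30 = 270 mg.

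These are doses that Section 5.6.2.1.2 would permit and Section 5.6.1.1 C would not. A longer taper raises the count.

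**Number of subjects.** This cannot be derived. Section 1.1.1 reports immune-mediated events in 22% of patients in one phase 1b pembrolizumab study, but not how many led to a hold. The protocol gives no hold or discontinuation rate for immune-mediated reactions on HBI-8000 combinations.

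**The case against.** The best defence is that the two sections can be reconciled. Section 5.6.1.1 C is a specific instruction, while Section 5.6.2.1.2 and the Synopsis are general permissions. A site that withholds HBI-8000 breaches neither, and a specific instruction is normally read over a general permission. Sections 4.5 and 5.6.2.1.1 both exclude immune-mediated reactions, so the intent is visible. This stands as a limit on severity. It does not remove the conflict, because a site relying on Section 5.6.2.1.2 has written permission to do what Section 5.6.1.1 C says not to do.

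A Synopsis is also allowed to condense. That has most force for the missing Medical Monitor consultation. It has less for the immune-mediated exception, because leaving that out changes what is permitted.

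A reader might infer that Section 3.1 is a third conflict, since it says "HBI-8000 will continue until disease progression, unacceptable toxicity related to HBI-8000 ensues or withdrawal of informed consent to receive HBI-8000". The documents do not support this. The same section also makes treatment conditional on the absence of unacceptable toxicity, without attributing it to either drug, and a design overview need not repeat a dose-modification rule.

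A reader might also infer that continued dosing has been shown to be harmful. Section 1.1.3.3 reports no evidence of immune-related toxicity beyond that expected with nivolumab alone, and Section 5.6.1.2 already lets the Investigator delay HBI-8000 for toxicity possibly or probably related to it. The point is the consistency of a safety rule.

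**Conclusion.** The point holds as an inconsistency of wording in a safety dosing rule, and it should be corrected. Section 5.6.2.1.2 permits HBI-8000 in a situation where Section 5.6.1.1 C says to hold it. The Synopsis lacks the same exception, and the consultation as well.

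Its size is bounded. For a lower-grade, steroid-treated irAE with a pembrolizumab hold, up to 8 to 9 doses (240 to 270 mg) would be permitted over a one-month taper. It would be wrong to read this as doses that will be given: the text is a permission. The figure also rests on HBI-8000 staying off as long as pembrolizumab. Section 5.6.1.1 C gives no restart time, and the taper is stated as a condition for resuming pembrolizumab only. The figure does not carry over to Grade 3 or greater irAEs, where the reduced dose and the 14-day recovery condition apply.

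The number of subjects affected is unknown. No stated figure, sample size or planned analysis changes.

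**What to change.** Two wording changes:

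1. **Section 5.6.2.1.2, last sentence.** Replace with: *Scheduled HBI-8000 dosing may go on during pembrolizumab interruptions that are not due to immune-mediated reactions; for immune-mediated reactions, withhold or discontinue HBI-8000 per Section 5.6.1.1 C.*
2. **Synopsis, Study Treatment, last sentence.** Replace with: *If toxicity other than an immune-mediated reaction is attributed to pembrolizumab, HBI-8000 may be continued at the Investigator's discretion in consultation with the Sponsor Medical Monitor; for immune-mediated reactions, follow Section 5.6.1.1 C.*

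Section 3.1 needs no edit. The new text should not send immune-mediated holds of more than 14 days to the Sponsor discussion in Section 5.6.1.2. That could be read as loosening the condition at the end of Section 5.6.1.1, under which HBI-8000 resumes only at a reduced dose after recovery to Grade 1 or less within 14 days.

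The cost is one protocol amendment, with IRB approval before implementation (Statement of Compliance; Section 8.3.6). It adds no procedures, visits or subjects.
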